12.5.3 Exploratory Analysis

12.5.3.1 Questionnaires

If feasible, all questionnaire endpoints will be analyzed in natural scale

12.5.3.1.1 Urge-to-Smoke Questionnaire of Smoking Urges Brief

All summaries, profiles and analysis will be presented for the CHTP 1.2 and CC arms.

The change from baseline will be calculated for the total score and the two domain scores (relief and reward). The total score and two domain scores, along with the change from baseline will be summarized (Table 15.2.5.1). The answers to the individual questions, along with the domain scores, total scores and changes from baseline will be listed (Listing 15.3.5.1).

The profiles of the arithmetic means and LS Mean differences per timepoint for the total score and two domain scores will be produced (Figure 15.1.3.1 and Figure 15.1.3.2).

The analysis will compare each post baseline timepoint in the domain and total scores. A repeated measures mixed model will be used with terms for baseline QSU-BRIEF score, sex, average daily CC consumption over the last 6 weeks as reported during admission, arm, timepoint, and the interaction between arm and timepoint. The interaction term will be removed if $p > 0.1$.

The SAS code will be the same as the repeated measures model described in Section “12.5.1.1 Primary endpoints”.

LS means for each arm along with the difference (CHTP 1.2 - CC) with 95% CI will be presented in table 15.2.5.2.

All figures, summaries and analyses will be performed on the Per Protocol Populations.

12.5.3.1.2 Modified Cigarette Evaluation Questionnaire

All summaries, profiles and analysis will be presented for the CHTP 1.2 and CC arm.

The change from baseline will be calculated for the five domain scores. The domain scores, along with the change from baseline will be summarized (Table 15.2.5.3). The answers to the individual questions, along with the domain scores and changes from baseline will be listed (Listing 15.3.5.2).

The analysis will compare each post baseline timepoint in the subscales. A repeated measures mixed model will be used with terms for baseline mCEQ score, sex, average daily CC consumption over the last 6 weeks as reported during admission, arm, time-point, and the interaction between arm and time-point. The interaction term will be removed if $p > 0.1$.

The SAS code will be the same as described in Section 12.5.2.1.3 “NEQ”.

LS means for each arm along with the difference (CHTP 1.2 - CC) with 95% CI will be presented in the table (Table 15.2.5.4).

The profiles of the change in arithmetic means and LS Means per time point for the five subscale scores will be produced (Figure 15.1.3.3 and Figure 15.1.3.4).

All figures, summaries and analyses will be performed on the Per Protocol Populations.

12.5.3.1.3 The Intent to Use Questionnaire (ITUQ)

The summaries will be presented for the CHTP 1.2 arm.

The answers to the individual questions will be tabulated (Table 15.2.5.5) and listed (Listing 15.3.5.3).

12.5.3.1.4 Fagerström Test for Nicotine Dependence (FTND)

All summaries, profiles and analysis will be presented for the CHTP 1.2 and CC arm.

The total score, along with the change from baseline will be summarized by means of descriptive statistics and a tabulation of the categorized total scores (Table 15.2.5.6). The answers to the individual questions, along with the total scores and changes from baseline will be listed (Listing 15.3.5.4).

The analysis will compare the Day 90 Visit values between the CHTP 1.2 and CC arms. An ANCOVA model will be used with terms for baseline, sex, average daily CC consumption over the last 6 weeks as reported during admission and arm. The SAS code will be the same as described in Section “**12.5.1.1 Primary endpoints**”; except that there will be no log transformation of the data (Table 15.2.5.7).

LS means for each arm along with the difference (CHTP 1.2 - CC) and 95% CI will be presented in the tables.

12.5.3.1.5 Prochaska “State of Change” Questionnaire: Intention to Quit Smoking

The stages of change will be cross-tabulated (screening vs Day 90 Visit) per arm (Table 15.2.5.8) and listed (Listing 15.3.5.5). The cross-tabulation will also be created per product use category (Table 15.2.5.8.1).

12.5.3.2 CYP2A6 Activity

If feasible, CYP2A6 will be analyzed in natural scale.

Descriptive statistics of the values and change from baseline on Day 6 and Day 90 Visit (Table 15.2.5.9) and supportive listings will be provided (Listing 15.3.5.6).

The analysis will compare the Day 6 and Day 90 Visit values between the CHTP 1.2 and CC arms. An ANCOVA model will be used with terms for baseline, sex, average daily CC consumption over the last 6 weeks as reported during admission and arm (Table 15.2.5.10).

The SAS code will be the same as described in Section “**12.5.1.1 Primary endpoints**”.

LS means for each arm along with the difference (CHTP 1.2 - CC) and 95% CI will be presented in the tables.

12.5.3.3 Ames Mutagenicity Test

It is assumed that Ames Mutagenicity Test is log-normally distributed.

The 24 hour urine collection for the Ames mutagenicity test will be on Day -1, Day 5 and Day 90 Visit.

Descriptive statistics of the values and change from baseline of the YG1024+S9 mutagenicity will be provided (Table 15.2.5.11), along with listings (Listing 15.3.3.1).

12.5.4 Safety Evaluation

Safety variables monitored in this study include: AEs; vital signs (systolic and diastolic blood pressure, pulse rate, respiratory rate); spirometry; ECG data; concomitant medication, clinical chemistry, hematology, urine analysis safety panel, BMI, physical examination, respiratory symptoms (cough assessment).

The primary analysis of Safety parameters will be conducted on the Safety Population as described in Section 12.1.3 “**Descriptive Statistics**”.

12.5.4.1 Safety Reporting

All safety data collected during the study will be provided in listings by randomization arm, subject and product use pattern category defined over the 3-month period. The safety time periods are defined in table **Table 7: Categorical Variables Definitions**”.

All summaries for safety parameters will be conducted on the Safety Population. Unless otherwise specified, summaries will be produced overall by randomization arm and by product use pattern categories

An exposure emergent AE is defined as an AE that occurs after first product use or that is present prior to first product use and becomes more severe after first product use. All other AEs will not be summarized but provided in listings only.

All AEs occurring from the time of signing of informed consent will be recorded electronically. AEs will be tabulated and listed. The AE listings will include all AEs captured in the database at any time during the study (including those from subjects who were not in the Safety Population).

AEs reported from subjects that have a first product use, but were not randomized will be summarized in a separate column with “Exposed but not randomized” as a column header.

Partial dates will not be imputed, but assumptions will be made as follows to assign to product-emergent or not (see section **12.1.5 Handling of Dropouts or Missing Data (including outside the limits of quantification)**).

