6.3.3.1 Dual Use

[figure not shown]
Although subjects are being requested to use solely the product allocated to them in their respective study arm, it is considered that during the ambulatory period not all subjects randomized to CHTP 1.2 arm might be exclusively using CHTP 1.2 at all times during the study. Subjects may concomitantly use CHTP 1.2 and CC (dual-use).

To assess dual-use of CHTP 1.2 and CC, PMI has defined product use categories defined by the percentage of the reported CHTP 1.2 Tobacco Sticks consumption during each time period of interest. The percentage use of CHTP 1.2 will be calculated by:

$$100 \times \frac{\text{Total number of CHTP 1.2 products used}}{\text{Total number of CHTP 1.2 products used} + \text{Total number of CC smoked}}$$

Product use categories are summarized in **Table 7**, and **Figure 2** presents a detailed overview of the definition of the product use categories.

Figure 2 Product Use Pattern Categorization

The more granular categorization scheme will be used for the description of the product use patterns observed in the study whereas the less granular scheme will be used for the presentation of other study endpoints (e.g. safety endpoints) to better understand the impact of product.

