12.1.5 Handling of Dropouts or Missing Data (including outside the limits of quantification)

For laboratory parameters:

- Values below the lower limit of quantification (LLOQ) will be imputed using LLOQ/2. For values above the upper limit of quantification (ULOQ), the ULOQ will be imputed.
- The number of values below LLOQ or above ULOQ will be presented in each summary table. If 50% or more data are below LLOQ or above ULOQ, only the number (%) of value below LLOQ or above ULOQ will be reported in the summaries, together with minimum and maximum of the observed values.
- Missing data at Baseline will not be imputed.

For daily product use data:

- If at least 75% of the daily product use assessments over a period are available, with no more than 7-days of consecutive missing data:
 - Product use categories will be defined based on percentage of THS 2.2 use calculated by averaging non missing consumption data over the analysis interval.
 - Compliance to randomized product will be defined based on the available product use data.
- If less than 75% of the daily product use assessments over a period are available, or product use data is missing over a period of more than 7 consecutive days:
 - Product use category and Compliance to randomized product will be considered missing.

For MNWS, QSU-brief, and mCEQ questionnaire data:

- Total scores and domain or subscale scores will be derived by averaging the individual non-missing item scores if at least 50% are non-missing, otherwise they will be set to missing.

For missing or partial dates:

- Missing dates for Day 30, 60, and Day 90 Visits will be imputed for the calculation of product use exposure within periods by adding 30, 60, or 90 days to the randomization date. If the imputed date falls after discharge date (e.g. for early terminated subjects), then the discharge date will be used.
- Missing or Partial dates will not be imputed for Adverse Events (AEs), for medical history, and for concomitant medications, but assumptions will be made as follows to assign them to specific analysis categories:

Date information (*)	AE Category	Disease Category	Medication Category
Missing date or Partial date, (e.g., --May2012, or ----2011) if month/year is the same as, or later than the month and/or year of Screening.	Product-emergent	Concomitant disease	Concomitant medication

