12.5.4.2 Adverse Events

12.5.4.2.1 All Adverse Events

All AE tables will be presented by randomization arm.

In general, AE summary tables reporting the number of events and the number and percentage of subjects reporting at least one AE will be produced by study arm and by product use pattern categories for the Pre-Randomization and Randomized periods.

In addition, AE data during the Randomized period will also be presented stratified by Confinement, Ambulatory, Safety Follow-up and overall (for the randomized period).

If a subject has more than one occurrence of the same AE, the subject will be counted only once within a PT with the worst occurrence for the incidence of that AE (e.g., by severity = severe, by relatedness = related to IP). If across all AEs, subject has more than one AE, subjects will be counted only once with the worst occurrence of his/her AEs. Missing attributes for seriousness are displayed as serious and missing severity as severe. The number of missing attributes are also displayed. Missing attributes for both relationship and study procedures are displayed as related to IP and not related to study procedures. For the prevalence of AEs, the breakdown by each severity and relatedness will be shown.

A general summary table of AEs (Table 15.2.6.1) will be presented including:

- The number of events and the number and percentage of subjects reporting at least one AE.
- The number of events and the number and percentage of subjects reporting at least one study product –related AE, broken down by product relatedness (related to CHTP 1.2 / CC) and expectedness.
- The number of events and the number and percentage of subjects reporting at least one AE broken down by severity including each subject only once with his worst severity.
- The number of events and the number and percentage of subjects reporting at least one SAE.
- The number of events and the number and percentage of subjects reporting at least one AE leading to any action taken, broken down by action taken related to the product (product use interrupted, product use reduced, product use withdrawn, none), treatment given (yes, no), study discontinuation, other action taken.

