15.2.5.3	Descriptive Statistics of modified Cigarette Evaluation Questionnaire Subscales – Per Protocol Population
15.2.5.4	Analysis of modified Cigarette Evaluation Questionnaire Subscales – Per Protocol Population
15.2.5.5	Descriptive Statistics of Intent to Use Questionnaire Subscales – Per Protocol Population
15.2.5.6	Descriptive Statistics of Fagerström Test for Nicotine Dependence – Per Protocol Population
15.2.5.7	Analysis of Fagerström Test for Nicotine Dependence – Per Protocol Population
15.2.5.8	Shift Table of the Prochaska Stages of Change – FAS
15.2.5.8.1	Shift Table of the Prochaska Stages of Change by Product Use Category– FAS
15.2.5.9	Descriptive Statistics of CYP2A6 Activity – Per Protocol Population
15.2.5.10	Analysis of CYP2A6 Activity – Per Protocol Population
15.2.5.11	Descriptive Statistics of Ames Mutagenicity Test (YG1024+S9) (units) – Per Protocol Population
15.2.6.1	Summary of Adverse Events – Safety Population
15.2.6.1.1	Summary of Adverse Events by Product Use Category– Safety Population
15.2.6.2	Summary of Adverse Events by System Organ Class and Preferred Term – Safety Population
15.2.6.2.1	Summary of Adverse Events by System Organ Class and Preferred Term with an incidence >5% in any Study Arm– Safety Population
15.2.6.2.2	Summary of Adverse Events by System Organ Class and Preferred Term by Product Use Category– Safety Population
15.2.6.3	Summary of Adverse Events by System Organ Class and Preferred Term by Product Use Safety Time Period– Safety Population

Tables	Title
15.2.6.4	Summary of Adverse Events by System Organ Class, Preferred Term and Relationship to Study Product Exposure for Investigational Product (CHTP 1.2 or CC) and Expectedness – Safety Population
15.2.6.5	Summary of Adverse Events Leading to Investigational Product (CHTP 1.2 or CC) Discontinuation by System Organ Class and Preferred Term – Safety Population
15.2.6.6	Summary of Adverse Events Leading to Study Discontinuation by System Organ Class and Preferred Term – Safety Population
15.2.6.7	Summary of Adverse Events Related to Study Procedure by System Organ Class and Preferred Term – Safety Population
15.2.6.8	Summary of Adverse Events by System Organ Class, Preferred Term and Severity – Safety Population
15.2.6.9	Summary of Serious Adverse Events – Safety Population
15.2.6.10	Summary of Serious Adverse Events by System Organ Class and Preferred Term and Severity – Safety Population
15.2.6.11	Summary of Clinical Chemistry Parameters – Safety Population

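### The adverse-event tables by product-use category label CHTP-arm subjects by use that can follow the event, so events on CHTP 1.2 can appear under CC or Dual

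*SAP*

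**What the plan says.** Protocol section 12.5.4 promises that safety variables from the exposure period will also be reported by product exposure. The SAP carries this out through product-use categories.

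- **Definition.** SAP 6.3.3.1 computes 100 × CHTP 1.2 sticks / (CHTP 1.2 sticks + CC) for each time period of interest. SAP Table 7 cuts this share, for the CHTP 1.2 arm only, into CHTP 1.2 (70% or more), Dual (between 30% and 70%) and CC (30% or less). The coarse scheme "will be used for the presentation of other study endpoints (e.g. safety endpoints) to better understand the impact of product".
- **Window.** SAP 12.5.4.1 says the safety listings are ordered by arm, subject and "product use pattern category defined over the 3-month period". The next paragraph adds that "summaries will be produced overall by randomization arm and by product use pattern categories", and names no other window.
- **Tables.** SAP 12.5.4.2.1 produces AE summaries "by study arm and by product use pattern categories for the Pre-Randomization and Randomized periods", and also presents the randomized period by confinement, ambulatory and follow-up phase. SAP 13.3.1 lists Table 15.2.6.1.1, "Summary of Adverse Events by Product Use Category– Safety Population", and Table 15.2.6.2.2, the same by system organ class and preferred term.
- **By arm.** SAP 12.5.4.2.1 also states: "All AE tables will be presented by randomization arm".
- **Incomplete diary.** Under SAP 12.1.5, with fewer than 75% of daily reports over a period, or more than 7 consecutive days missing, "Product use category and Compliance to randomized product will be considered missing".
- **Participation.** Under SAP 6.1 and Protocol 6.3.4, smoking cigarettes in the ambulatory period does not end participation.

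**The concern.** A category computed over the whole exposure period mixes use before the event with use after it, and the event can influence the later use. Suppose a subject has nausea or cough on CHTP 1.2 in week 2 and goes back to cigarettes. The subject ends with a low CHTP 1.2 share, and the event is shown in the CC column of the CHTP 1.2 arm.

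Confinement is the clearest case and needs no causal link. Under Protocol 6.3.3 and 6.6.1, CHTP-arm subjects use only CHTP 1.2, dispensed stick by stick, until discharge on Day 6. A Day 3 event is an event on CHTP 1.2, yet it would be labelled by what the subject does over the following weeks.

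At stake is the reading of two tables whose purpose is to show the product's impact. Where events drive the switch, the CHTP 1.2 column looks better tolerated than it was and the other two look worse. Where the switch is unrelated to the event, the exposure label is still wrong, but the bias need not run in one direction.

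**Working it through.** The plan gives no figure of its own on this point. The check applies the SAP's ratio and cut-offs to a subject who uses only CHTP 1.2 up to and including day T and only CC from then to Day 90.

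**Inputs.** Ratio from SAP 6.3.3.1; cut-offs 30% and 70% from SAP Table 7; exposure to Day 90, with discharge from confinement on Day 6.

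**Assumptions.** The window is either Days 1–90 or the ambulatory Days 6–90 (85 days), since the SAP does not say which. Daily CC use is r times earlier daily CHTP 1.2 use, with r = 1 and a range of 0.75 to 1.25.

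**Formula.** Share = h / (h + r × (90 − T)), with h = T for Days 1–90 and h = T − 5 for Days 6–90.

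For r = 1 the limits are:

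- Days 1–90: 0.30 × 90 = 27 and 0.70 × 90 = 63.
- Days 6–90: 5 + 0.30 × 85 = 30.5 and 5 + 0.70 × 85 = 64.5.

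| Window | r | Last CHTP 1.2 day giving CC | giving Dual | giving CHTP 1.2 |
|---|---|---|---|---|
| Days 1–90 | 0.75 | up to 21 | 22–57 | 58 or later |
| Days 1–90 | 1.00 | up to 27 | 28–62 | 63 or later |
| Days 1–90 | 1.25 | up to 31 | 32–67 | 68 or later |
| Days 6–90 | 0.75 | up to 25 | 26–59 | 60 or later |
| Days 6–90 | 1.00 | up to 30 | 31–64 | 65 or later |
| Days 6–90 | 1.25 | up to 34 | 35–68 | 69 or later |

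Example: the last CHTP 1.2 day is Day 20. The share is 20/90 = 22% or 15/85 = 18%, so CC under either window.

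**Who is not relabelled.** If no CC is smoked, the CC term is zero and the share is 100%. A subject who stops all tobacco, or leaves without smoking, does not move to CC or Dual.

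**Period-specific reading.** If the category were computed per period, Period 2 would run over about Days 6–30 (25 days). With r = 1, a last CHTP 1.2 day of 12 gives 7/25 = 28% (CC); Day 13 gives 8/25 = 32% and Day 22 gives 17/25 = 68% (both Dual). A week-2 event followed by a switch to CC still leaves the CHTP 1.2 column.

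**Missing category.** 75% of 85 days is 63.75, so 64 reports are needed; 75% of 90 is 67.5, so 68. If the denominator is the full 3 months, anyone leaving before about Day 68–69 has no category. If the period ends at discharge, an early leaver can keep one. Neither SAP Table 7 nor Table 16 has a missing level.

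**Illustration (assumed counts).** Take 80 CHTP-arm subjects, 8 with an event, of whom 4 then switch early to CC, and no other switchers. By arm: 8/80 = 10.0%. In the CHTP 1.2 category: 4/76 = 5.3%. With 20 further event-free subjects in Dual or CC: 4/56 = 7.1% against 4/24 = 16.7%.

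**The case against.** **The 3-month phrase is about listings.** A reader might infer that the SAP fixes this window for the tables. It does not: the sentence on summaries names no window, and SAP 6.3.3.1 leaves room for period-specific categories. This objection stands as to wording. Two things limit it. No other window is given in the safety section, and splitting the pre-randomization period by category makes sense only if the label comes from later behaviour. The period-specific reading also does not remove the problem.

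**No event is lost.** This stands. Every AE table is also presented by arm. Table 15.2.6.5 covers events leading to product discontinuation, Table 15.2.6.4 relatedness and Table 15.2.6.3 time period. The CC category lies inside the CHTP 1.2 arm, so nothing moves to the CC arm. The category tables are descriptive and are in neither the topline set nor the ClinicalTrials.gov set. But none of the tables just named splits the CHTP 1.2 arm by product actually used, which is what the category tables are for.

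**Uncategorised subjects.** A reader might infer that they drop out of these tables. The documents do not say so: SAP 12.1.5 calls the category missing and is silent on display. This is a gap in the plan, not a stated exclusion.

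**Not every event that ends CHTP 1.2 use is moved.** Correct. Relabelling needs continued participation, cigarette smoking, and a switch early enough in the window.

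**The day limits do not measure impact.** Also correct. They show which switches change a label, not how many subjects or events move.

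**Conclusion.** The point holds in a limited form. The two by-category AE tables use a post-randomization label that, on the most natural reading of SAP 12.5.4, covers the whole 3 months and so includes use after the event. Events during exclusive CHTP 1.2 use in confinement, and early ambulatory events followed by a switch to CC, are then shown under CC or Dual within the CHTP 1.2 arm.

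Allowing for both windows and for CC use at 0.75 to 1.25 times CHTP 1.2 use, the latest last CHTP 1.2 day giving CC lies between Day 21 and Day 34, and the latest giving Dual between Day 57 and Day 68. These limits assume a single permanent switch and constant daily rates. The number of events affected cannot be derived from the documents; the illustrative percentages are not estimates.

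The randomized comparison of adverse events is not affected. What is unreliable is any reading of the category columns as safety by exposure.

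**What to change.** For Tables 15.2.6.1.1 and 15.2.6.2.2 only, state the window and assign each event by product use up to the day before onset:

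- **Product-test events:** show separately.
- **Confinement events:** assign by product dispensed.
- **Ambulatory events:** assign by CHTP 1.2 share from the start of the Product Use Safety Time Period (SAP Table 7) to the day before onset, or from the previous period if onset is on its first day.
- **Safety follow-up events:** assign by the last available category, because the Table 7 periods end at the Day 90 Visit.
- **Not classifiable:** add a column with its n for events without a usable share.

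Report event counts with subject-days in each category as denominator, classifying days by the same rule as events. Event counts then sum to the arm total; subject counts will not. State that the by-arm tables remain the basis for safety conclusions.

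The cost is SAP wording and programming. Logs, diaries and AE onset dates are already collected. If the database is already locked, SAP 13.3 allows this as a documented additional analysis. There are two downsides: a subject can appear in more than one category, and shares based on only a few days are unstable.
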